Acute Alcohol Effects. Acute alcohol intake at legally intoxicating levels (i.e., BAC \geq 0.08 g/dL) is associated with robust decrements in inhibitory control (Dougherty et al., 2008; Fillmore and Weafer, 2004; Loeber and Duka, 2009), psychomotor performance (Harrison and Fillmore, 2005), attentional function (Marczinski and Fillmore, 2006), and

working memory processes (Soderlund et al., 2005; Weissenborn and Duka, 2000). Even subintoxicating blood alcohol concentrations (BACs) can selectively disrupt neuropsychological processes critical for the processing of nociceptive stimuli, including sustained and/or divided attention, inhibitory control, and working memory ([name] et al., 2014; [name] et al., 2016; Breitmeier et al., 2007; de Wit et al., 2000; Friedman et al., 2011; Gilbertson et al., 2009; Holloway, 1994; Lloyd and Rogers, 1997). Numerous factors besides dose may modulate the effects of acute alcohol. Critically, expectations regarding the positive and negative effects of a given alcohol dose are important predictors of its neurobehavioral effects. Numerous studies indicate expectation of impairment is an important predictor of behavioral compromise following alcohol administration (Field et al., 2008; Fillmore et al., 1998; Marczinski and Fillmore, 2005) and almost certainly contributes to alcohol's analgesic effects as well. In addition, individuals with a family history of alcoholism (FH+) have atypical subjective responses to alcohol, with competing models describing either consistently lower levels of response to alcohol challenge, or increased stimulation on the ascending limb combined with decreased sedation on the descending limb (Morean and Corbin, 2010; Schuckit, 1994).

Studies of the neurophysical and functional correlates of alcohol-induced neurobehavioral compromise indicate disruption of functional activation and glucose utilization in brain structures including anterior cingulate gyrus, prefrontal cortex, medial frontal cortex, and the basal ganglia (Anderson et al., 2011; Marinkovic et al., 2012; Soderlund, et al., 2005, Volkow et al., 2006). Notably, these areas and the evaluative, limbic, and executive networks they form are implicated as modulators of acute and chronic pain, suggesting a common neural framework underlying both acute alcohol effects and the pain experience (Hashmi et al., 2013).

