Aim 2. Determine the influence of typical alcohol use and expectation of pain relief with alcohol use on magnitude of alcohol analgesia and associated feelings of relief. Studies of alcohol analgesia in healthy adults have indicated that individual patterns of typical alcohol use, motivation to drink, and personality factors may modulate alcohol analgesia, suggesting a critical role of conditioning and expectancies (Brown and Cutter, 1977; Cutter et al., 1979; Ralevski et al., 2010). However, this question has never been directly examined, either in healthy adults or those with chronic pain. **H4.** We predict individuals with stronger positive expectancies regarding alcohol analgesia will have significantly stronger analgesic responses to alcohol administration. **H5.** Based on previous research, we predict that individuals who endorse greater and more frequent alcohol consumption will experience a greater analgesic effect of alcohol, independent of the effect of expectancies. Finally, we ask as **E2.** whether chronic pain status will be associated with stronger expectancies of pain relief following alcohol consumption and **E3.** greater ratings of pain relief during pressure algometry after drinking.

6. Research Plan:

General Approach. For this study of current non-problem drinkers, we propose a repeated-measures, double blind placebo-controlled factorial design with chronic pain status (TMD vs. healthy control) as a between-subjects factor and alcohol administration (Alcohol Dose: placebo, 0.08 g/dL) as a within-subjects factor. The study will include both men and women. Study procedures will occur at the Center for Pain Research and Behavioral Health of the University of Florida under supervision of the PI (JB).

Methods

Participants. Individuals seeking care for temporomandibular joint and muscle disorder (TMD) (n=25) will be recruited for the study via flyers, word of mouth, internet/local radio advertisements, and [name] orthodontic clinic. A sample of healthy social drinkers without TMD (HC) will also be recruited as a comparison group (n=25). Individuals aged 21-45 years will be recruited to avoid any vulnerability to acute neurobehavioral effects of alcohol associated with older age (e.g., [name] et al., 2016a). Because TMD is more prevalent in women than men (~2:1; Campbell et al., 2017), we anticipate the final sample will consist of approximately 2/3 women.

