
Alcohol Administration. Alcohol administration procedures are consistent with our previous work and NIAAA guidelines for the safe and ethical administration of alcohol in

experimental settings (Brown et al., 2014). Participants will complete two laboratory sessions in which they will be administered one of two beverages: placebo (0.00 g/dL target BrAC) or active alcohol (0.08 g/dL target BrAC). Session order will be counterbalanced across participants. For laboratory sessions in which a participant will be given the active dose, the quantity of medical/United States Pharmacopeia grade alcohol (100% or 95% ethanol) needed to achieve 0.08 g/dL (i.e., approximately 3-4 standard drinks) will be calculated using a modification of the Widmark formula. This formula utilizes age and weight measures for men and height and weight measures for women (Watson, et al., 1981; Widmark, 1932). For example, a 30-year old man who is 183 cm tall and weighs 75 kg would receive 55.3 ml of absolute ethanol, or ~.58 g/kg. In order to maintain the study's double blind, a researcher not involved in QST will be responsible for calculating alcohol doses and mixing drinks, and the dose calculation and mixing procedure confirmed by a second research assistant. Pre-calculated dose lookup tables indexing height and weight for women and age and weight for men will be used to avoid dosing errors. Alcohol will be mixed with cold sugar-free lemon-lime soda in a 1:3 ratio and split into two servings ([name], et al., 2014; Gilbertson, et al., 2009; Harrison et al., 2007). Placebo beverages will consist of only soda. Participants will consume both servings within 5 minutes. **Both active and placebo drinks will be misted with alcohol to enhance placebo effectiveness. A small amount of alcohol will be placed on the rim of the glass and floated on the surface of the beverage to further mask the study condition.** Participants will rinse their mouths thoroughly with water once their beverage has been consumed. No suggestion regarding the potential pain-relieving effects of alcohol will be provided before or after beverage administration to avoid influencing expectations. All study staff over the age of 21 designated as "Interacts or intervenes directly with study subjects" on the myIRB smart form will be trained by the PI how to use the lookup tables and mix beverages and may serve in this capacity depending on availability for a given laboratory session.

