BrAC Assessment. Following beverage administration, breath alcohol concentration (BrAC) measures will be obtained every 10 minutes, as well as immediately prior to and after QST, using standard a handheld breath analysis device (e.g., Intoxylizer 400PA, CMI, Inc., Owensboro, KY). Breath measures will be taken periodically until the participant's BrAC is ≤ 0.02 (Brown et al., 2014). They will then be transported home.

Subjective Intoxication and Placebo Effectiveness. Participants will complete brief visual analog scales (VAS) assessing their subjective intoxication (anchored from 'not at all intoxicated' to 'most intoxicated imaginable'; Harrison, et al., 2007). These assessments will be administered concurrently with BrAC assessments and before/after QST. To assess the contribution of subjective stimulatory/depressant effects to alcohol analgesia, the Subjective Effects of Alcohol Scale (SEAS; Morean et al., 2013) will be administered immediately prior to QST. The SEAS measures both positive and negative aspects of stimulation and sedation (i.e., HIGH+/- and LOW+/-). After testing, participants will indicate whether they believe they received an alcoholic beverage; those who do not believe they received a beverage will be asked when they made that determination.

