Pain Induction Procedure. QST testing will occur in a private room within the Center for Pain Research and Behavioral Health using an approach developed by our research group (Brown et al., 2000). Pain induction will involve application of manual pressure to the insertion of the masseter muscle, 1 cm superior and anterior to the angle of the mandible. This location will be marked with ink to ensure a consistent stimulation site. For participants with TMD, pressure will be applied to the most affected (i.e., sensitive) side of the face, as determined during [name] examination. For control participants, the side of the face to be stimulated will be randomly determined. [name] will train the PI and all research assistants (RAs) to ensure consistent localization of this point across participants. Pressure will be increased over a 1s duration and maintained for 2s using a Wagner Force One pressure algometer (Wagner Instruments, Greenwich, CT). VAS pain intensity and unpleasantness ratings (anchored from "no pain at all"/"not at all unpleasant" to "most intense/unpleasant imaginable") will be collected. Ratings will be collected at 4, 5, and 6 foot pounds per square inch (fpsi). Pain ratings will also be collected 15 and 30 seconds after algometer removal to assess aftersensation. This procedure will be repeated three times, with pressures alternated in pseudorandom order. Mean pain ratings at each stimulation level will be used to calculate individualized slopes (representing discriminability between pressure stimuli) and intercepts (representing response bias) for each participant and treatment condition (i.e., active alcohol vs. placebo) (Brown et al., 2000). Pain threshold will also be assessed by increasing pressure on the masseter insertion at a rate of .5 fpsi/s. Participants will indicate when the sensation first becomes painful and provide a VAS rating of pain intensity at the threshold pressure. This procedure will also be repeated three times and threshold and pain intensity measures will be calculated as the mean of the three trials. Following each QST measure, participants will be provided with a 10 cm VAS assessing perceived relief from pain resulting from beverage consumption (anchored from "No relief at all" to "Most profound relief imaginable"). QST procedures will require approximately 15 minutes. During laboratory sessions, QST procedures will begin approximately 15 minutes after beverage consumption to allow for absorption of alcohol ([name] et al., 2014).

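### One BrAC release rule for both drinks makes length of stay an avoidable cue to the session 1 drink, and the plan neither records belief before the session 2 drink nor models session order

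*Combined protocol and SAP*

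**What the plan says.** All references are to section 6 (Research Plan) of the combined protocol and SAP unless stated.

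- General Approach calls the study a "repeated-measures, double blind placebo-controlled factorial design", with dose as the within-subject factor.
- Alcohol Administration: "Participants will complete two laboratory sessions in which they will be administered one of two beverages", namely "placebo (0.00 g/dL target BrAC) or active alcohol (0.08 g/dL target BrAC"). "Session order will be counterbalanced across participants". The masking steps concern the drink (alcohol mist, rim and surface) and who mixes it. None concerns how long the participant stays.
- BrAC Assessment: breath measures continue "until the participant's BrAC is ≤ 0.02 (Brown et al., 2014). They will then be transported home". The rule is the same for both drinks, and no minimum or common stay is given.
- Pain Induction Procedure: "QST procedures will begin approximately 15 minutes after beverage consumption to allow for absorption of alcohol". Testing lasts about 15 minutes. Laboratory Sessions adds lunch after testing, a further light meal if needed, and at least 48 hours between sessions.
- Subjective Intoxication and Placebo Effectiveness: "After testing, participants will indicate whether they believe they received an alcoholic beverage". Those who think their drink was not alcoholic are then asked at what point they reached that view.
- Data Analysis Strategy: the repeated-measures model has dose as the repeated factor and chronic pain status between subjects. It has no session or order term and makes no use of the belief answers.
- Section 4 (Background, Acute Alcohol Effects) says that expectation "almost certainly contributes to alcohol's analgesic effects as well".

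**The concern.** With two sessions and two drinks, knowing the first drink identifies the second for anyone who knows that each is given once. The release rule holds participants for hours on one day and imposes no wait on the other. It could therefore confirm the session 1 drink at discharge, after session 1 testing is over and before session 2 begins.

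The protocol itself regards expectation as part of alcohol analgesia. If participants start session 2 knowing their drink, the session 2 contrast compares known alcohol with known placebo, and the estimates for H1 (pain sensitivity) and H2 (perceived relief) take in extra expectancy. The relief scale is especially exposed, because it asks about relief caused by the beverage. With no order term and no planned use of belief data, a dose effect that differed between sessions would not be seen.

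**Working it through.** **Plan's own figure.** Paired t test, N = 50, d = 0.58, two-sided alpha .05: noncentrality 0.58 × √50 = 4.10, power 98.0%. This reproduces the stated 98%. The d of .58 serves below only as a yardstick.

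**Length of stay.** Placebo day: 0.00 is below 0.02 at every reading, so the rule imposes no wait. Testing ends about 15 + 15 = 30 minutes after the drink, then lunch. Active day: hours to release = (starting BrAC − 0.02) / rate of fall. The documents give no rate, so a range is assumed.

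| Assumed rate (g/dL per hour) | From 0.08 | From 0.06 (target missed) |
|---|---|---|
| 0.010 | 6.0 h | 4.0 h |
| 0.015 | 4.0 h | 2.7 h |
| 0.020 | 3.0 h | 2.0 h |
| 0.025 | 2.4 h | 1.6 h |

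The wait that the rule imposes is more than an hour and a half throughout.

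**Unblinding across sessions, all cues together.** Assumptions, none from the documents: with an intact blind, 95% believe they had alcohol on the active day and a proportion p of 0.5 to 0.8 believe so on the placebo day. With full unblinding in session 2 these become 100% and 0%. Believing one has had alcohol shifts the outcome by 0.2 to 0.5 SD of the paired difference.

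- Growth in the belief gap, averaged over two sessions = [1 − (0.95 − p)] / 2 = 0.275 at p = 0.5 and 0.425 at p = 0.8.
- Shift: 0.275 × 0.2 = 0.055 SD, up to 0.425 × 0.5 = 0.2125 SD.
- Relative to 0.58: about 9% to 37%.

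For scale, with no true effect, an average shift of 0.10 to 0.20 SD would make the paired test at N = 50 reject in about 11% to 28% of trials instead of 5%.

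**Share due to the release rule alone.** Keep the 95%, and suppose participants know they get one of each drink.

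- Alcohol first: 95% already recognise alcohol in session 1 and so expect placebo in session 2. Belief in alcohol on that placebo day is about 5% without any discharge cue, and 0% with it.
- Placebo first: belief on the session 2 active day goes from 95% to 100%.
- Growth in the gap = (0.05 + 0.05) / 2 = 0.05. Shift: 0.05 × 0.2 = 0.01 SD to 0.05 × 0.5 = 0.025 SD. Relative to 0.58: about 2% to 4%.

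In general this increment is 1 minus the active-day belief rate, so it would be larger if intoxication were less recognisable than assumed.

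**Precision of a session-1-only check.** Counterbalancing 50 participants gives 25 v 25. Standard error = √(2/25) = 0.28 between-person SD. Detectable d at 80% power, two-sided .05, is about 0.81.

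**The case against.** A reader might infer that the release rule by itself unblinds every participant for session 2 and inflates the alcohol effect by 9 to 37%. The documents do not support that, for these reasons.

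- Intoxication comes first. The active drink is about 3 to 4 standard drinks given to current drinkers. If 95% recognise it, nearly all alcohol-first participants can infer their session 2 placebo without a discharge cue. This stands, and it is why the release-rule share is only 2 to 4%. Discharge might also turn belief into certainty, but that is not modelled here.
- What participants are told cannot be seen, because the consent text is not in the available documents. If they do not know that each drink is given once, learning the first does not reveal the second. This stands: unblinded entry to session 2 is conditional.
- The placebo-day length is not stated. The protocol schedules rides after the session is complete, and a first-session participant has no earlier stay to compare with. This stands in part: early departure is what the rule permits, not what the text prescribes.
- The belief question is not confined to session 1, and its follow-up on timing can pick up an alcohol-first participant who decided before drinking in session 2. This stands in part. That follow-up goes only to those who think they had no alcohol, and it is asked after the pain ratings.

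A reader might also infer that H4 is directly inflated. Analgesia expectancies are measured at screening, before any drink, and no figure supports that step.

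None of this supplies a common stay, a belief measure before the session 2 drink, or an order term.

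**Conclusion.** The concern holds in a limited form. Length of stay is an avoidable extra cue to the session 1 drink, and the plan has no means of showing whether the blind survives into session 2. That matters for a trial that claims a double blind and expects expectation to contribute to the effect.

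Unblinding across sessions from all cues could add 0.06 to 0.21 SD (9 to 37% of d = .58). The release rule on its own adds about 0.01 to 0.025 SD (2 to 4%). Both ranges rest on the assumed belief rates and belief effects, and the second also on participants knowing they receive one of each drink. The difference of hours in required stay rests on the assumed rate of fall. Session 1 ratings are not touched by the discharge cue, because testing precedes discharge, but they remain open to intoxication cues.

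**What to change.** 1. In session 2, before the drink is served, ask which beverage the participant thinks they had last time and which they expect now. Cost: one short question.
2. Add session order to the repeated-measures model, and report a session-1-only alcohol v placebo comparison as a sensitivity check. With order as a between-subject factor, its main effect reflects any difference in the dose effect between sessions (mixed with carryover), and dose by order reflects the session effect. State beforehand that the session 1 comparison is imprecise (standard error about 0.28 SD, detectable d about 0.81), so it is a check and not a replacement. Its SD is between persons and is not the paired-difference SD behind d = .58. Cost: analysis only.
3. State the rule for interpretation: if session 2 beliefs show unblinding, or the session 1 estimate is clearly smaller, describe the crossover effect as pharmacological plus expectancy. Given the precision, the belief data will usually be the more informative of the two.
4. Where feasible, announce the same standard session length and breath-check timetable for both days, and do not show participants their readings. Leave the safety release criterion unchanged. Cost: a longer placebo-day stay, possibly by hours. A common length shorter than the slowest active-day release would leave some of the cue in place. This item is secondary to the first three.

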
Data Analysis Strategy. Data will be analyzed using SPSS 24 (IBM Corp., Armonk, NY).

Aim 1. Determine the effect of chronic pain status on magnitude of alcohol analgesia and associated feelings of relief. To assess hypotheses and empirical questions related to Aim 1, chronic pain status will be included as an independent variable in repeated measures general linear models analyses (rmGLM; SPSS GLM procedure; repeated: dose), with QST measures, associated relief ratings, and SEAS measures as dependent variables. Demographic, personality/affective (i.e., BDI/STAI/IRQ/BFI), substance use-related (recent alcohol use/alcohol use disorder symptomatology), pain-related (TMD severity), and biological (i.e., approximated menstrual phase for female participants) variables will be included as covariates should any correlate significantly with magnitude of alcohol analgesia or relief ratings.

Aim 2. Determine the influence of typical alcohol use, and alcohol analgesia-related expectancies on magnitude of alcohol analgesia and associated feelings of relief. A combination of approaches will be used to address Aim 2. Simultaneous multiple regression of alcohol analgesia expectancy and typical alcohol consumption

(estimated in ounces of absolute ethanol consumed per day derived from the AUQ) on QST measures will be used to evaluate H4 and H5. As in Aim 1, rmGLM will be used to assess E2 and E3.

Power Analysis. Power analyses for the proposed work are based on effect sizes derived from our initial feasibility study (see attached grant application for details) and were performed assuming two-tailed hypothesis tests with alpha=.05. Effect sizes are reported as Cohen's d, Pearson's r, or R2 (Cohen, 1988). Analyses indicated N=50 would provide excellent (98%) power to detect analgesic effects of alcohol administration on QST measures (Cohen's d > .58) and correlations between VAS ratings of relief and alcohol analgesia (r = .64). Critically, this sample size will also provide 80% power to detect small-to-medium sized effects (d > .40; r > .37; R² > .14) for which prior estimates are not available (e.g., the effect of chronic pain status on alcohol analgesia and subject alcohol affects). *We will recruit a total of 60 qualified subjects over the course of the project to account for 10% anticipated participant dropout before completing all study visits.*

7. Possible Discomforts and Risks:

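### No centring rule or H1/H2 contrast is stated for the covariate-adjusted repeated-measures GLM; with covariates entered as recorded, the dose row would test alcohol's effect at covariate = 0

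*Combined protocol and SAP*

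**What the plan says.** The plan is in section 6 (Research Plan) of the combined protocol and SAP.

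- General Approach makes dose a two-level factor: "alcohol administration (Alcohol Dose: placebo, 0.08 g/dL) as a within-subjects factor".
- Data Analysis Strategy, Aim 1, names the model: "chronic pain status will be included as an independent variable in repeated measures general linear models analyses (rmGLM; SPSS GLM procedure; repeated: dose"). The outcomes are the QST measures, the relief ratings and the SEAS measures.
- The same paragraph lists demographic, affective, alcohol-use, TMD-severity and menstrual-phase variables, which "will be included as covariates should any correlate significantly with magnitude of alcohol analgesia or relief ratings".
- Power Analysis assumes "two-tailed hypothesis tests with alpha=.05" and states: "Analyses indicated N=50 would provide excellent (98%) power to detect analgesic effects of alcohol administration on QST measures (Cohen's d > .58").

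Section 5 gives the hypotheses. H1 is less pain sensitivity under alcohol than placebo in both groups, H2 is greater relief under alcohol, and H3 is a difference between groups in the alcohol effect.

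The documents do not say whether continuous covariates are centred. They also do not say which output decides H1 and H2: the dose row, a contrast at the covariate means, or a contrast within each group.

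**The concern.** H1 and H2 ask about the average alcohol-placebo difference. Once a covariate is in the model, the dose row answers that question only if the covariate is centred. With a covariate on its recorded scale, the row estimates the effect for a person whose covariate value is 0. No participant can have age 0.

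The entry rule adds to the exposure. A covariate that enters because it correlates with the alcohol-placebo difference is one for which the effect at 0 departs from the average effect.

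Two analysts could both follow Aim 1 faithfully, one centring and one not, and reach different conclusions on the main alcohol-versus-placebo hypotheses. Nothing in the plan would settle which was right, and the choice could be made after seeing the results.

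**Working it through.** **1. The plan's own figure.** Inputs from Power Analysis: N=50, d=.58, two-sided alpha .05. A paired test has noncentrality .58 × √50 = 4.10. The normal approximation gives Φ(4.10 − 1.96) = 98.4%, and the noncentral t gives 98.0%. The stated 98% reproduces for a dose test without covariates.

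**2. What the dose row tests.** Let D be a participant's alcohol-placebo difference, signed so that positive means analgesia. With two dose levels, the repeated-measures dose test is the test of b0 in

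D = b0 + b1·group (effect-coded) + b2·covariate + error.

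On a simulated data set, the dose F was identical in this regression and in the full repeated-measures model, with the covariate raw and with it centred. Scale D to SD 1 and let r be the covariate's correlation with D. Then:

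- covariate centred: b0 = d, the average effect;
- covariate raw: b0 = d − r × (mean/SD).

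Centring leaves the group-by-dose test unchanged (t differs by less than 1e-13).

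**3. Age as the example.** Eligibility is 21-45 years. Assuming a uniform distribution, the mean is 33, the SD is 24/√12 = 6.93 and mean/SD is 4.76. With d=.58 and r=+.30, the raw-age row tests .58 − .30 × 4.76 = −.85, which has the opposite sign. The standard error at age 0 is about √(1 + 4.76²) = 4.9 times that at the mean.

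**4. Simulation with the plan's entry rule.** Settings: 25 + 25 participants; age enters only if p<.05, which at N=50 means |r| > .279; otherwise the model without covariates is used. The values of r are assumptions, because the documents give none.

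| True d | r | Age enters | Raw age, given entry | Raw age, overall | Centred |
|---|---|---|---|---|---|
| .58 | +.30 | 57% | 0% correct, 41% reversed | about 40% correct, about 24% reversed | 98-99% correct |
| .58 | −.30 | 57% | nearly all correct | about 99% correct | 98-99% correct |
| .58 | 0 | 5% | about 50% correct, 5-6% reversed | about 96% correct, 0.3% reversed | 98% correct |
| 0 | ±.30 | 57% | about 90% reject | about 55% reject | 6-7% reject |
| 0 | 0 | 5% | 77% reject | about 8% reject | 5-7% reject |

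The overall column follows from the conditional one:

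- Row 1: .43 × .98 = .42 correct and .57 × .41 = .23 reversed.
- Row 3: .05 × .50 + .95 × .98 = .96.
- Row 4: .57 × .91 + .43 × .05 = .54.
- Row 5: .05 × .77 + .95 × .05 = .086.

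**5. A milder covariate.** Assume mean/SD = 1.2. With d=.58 and r=+.30 the raw row tests .58 − .30 × 1.2 = .22. Power is about 5% given entry and about 44% overall, and a significant reversal occurs in 0.3% of trials given entry. With no average effect, rejection given entry is about 60% at |r|=.30 and about 40% at r=0.

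**6. Number of candidates.** With 10 independent null candidates, the chance that at least one enters for a single outcome is 1 − .95^10 = 40%. The 5% entry rate in the r=0 rows is therefore a lower bound for a plan that lists several classes of covariate.

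**The case against.** The strongest reply is that the plan never says covariates enter uncentred. That is right. A reader might infer a documented wrong step from the named procedure, but the text is silent, so the defect is an unspecified rule.

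A second reply is that H1 speaks of both groups, which points to within-group contrasts as much as to the pooled dose row. A contrast or marginal mean evaluated at the covariate mean avoids the problem. That also stands, but the plan specifies no such contrast.

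Third, the most striking percentages are conditional on a covariate entering. For one null age-like covariate the overall cost is small. Large overall effects need a true correlation, which nothing in the documents supports or excludes, and the effect on power depends on its sign: r=−.30 costs nothing.

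Fourth, not every candidate behaves like age. A categorical variable entered as a factor is not distorted in this way. AUDIT is capped below 8 and BDI-II below 20 by eligibility, so 0 is an attainable value and sign reversal is unlikely.

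These points limit the size of the problem. They do not remove it, because the loss of power and the false positives in step 5 arise without any reversal.

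**Conclusion.** The concern holds as a gap in specification that has a real consequence. If continuous covariates enter as recorded and H1 and H2 are read from the dose row, the tests no longer address the average alcohol effect. Under the age assumptions and |r|=.30, a trial with no average effect rejects about 55% of the time overall. A trial with d=.58 keeps between about 40% and about 99% power, depending on the sign of r. With a single null age-like covariate the figures are about 96% power and about 8% false positives, and the harm grows with the number of candidates.

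Two stronger readings are not supported. One is that H1 and H2 will be reversed: this needs an age-like covariate, a true correlation of the harmful sign, raw entry and reliance on the dose row. The other is that the 98% power is wrong: it is correct without covariates or with centred ones, and fails only for the raw-covariate dose row. H3 is not touched.

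The percentages rest on assumed covariate distributions and correlations. The algebra in step 2 does not.

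**What to change.** Add to Data Analysis Strategy, Aim 1, before the data are analysed:

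- Continuous covariates are centred at the mean of the analysed sample before entry.
- H1 and H2 are tested as the alcohol-placebo contrast at the covariate means, overall and within each group.
- The dose test without covariates is reported beside the adjusted one.
- Categorical covariates enter as factors. If sex is one, state the weighting, for example sample proportions. About two thirds of the sample are expected to be women, so a dose effect that weights the sexes equally is not the sample-average difference.
- Menstrual phase, defined only for women, is used only in a women-only sensitivity analysis.

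The cost is a few sentences. Data collection, sample size and participant burden do not change. Centring does not remove the data-driven selection of covariates, which is why the test without covariates should always be shown.
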